			13. Removed analysis using the per-protocol set	16. Section 2.6.2 Statistical hypothesis, model, and method of analysis
			14. Removed analysis of percent change from baseline and Month 6 re-baseline in lesion volume parameters	17. Section 2.7.1 Adverse events (AEs)
			15. Clarified determination of number of new/enlarging T2 lesions for derivation of annualized new/enlarging T2 lesion rate	18. Section 2.7.1 Adverse events (AEs)
			16. Removed observed case approach for summarization of participants with confirmed relapses	19. Section 2.7.1.1 Adverse events of special interest / grouping of AEs
			17. Added summaries for treatment-related SAEs and AEs occurring with frequency >5%	20. Section 2.10 Patient-reported outcomes
			18. Added details regarding summarization of AEs needed for ClinicalTrials.gov and EudraCT	21. [REDACTED]
			19. Removed summary of infection-related AEs	22. [REDACTED]
			20. Clarified that only total raw score for NeuroQOL Communication short form domain will be summarized	23. [REDACTED]
			21. Indicated that analysis of NfL values will not occur for the Month 18 interim analysis; NfL values will be analyzed at the time of the final analysis for the study	24. [REDACTED]
			22. [REDACTED]	25. Section 4 Change to protocol specified analyses
				26. Section 5.1.3.3 Other imputations
				27. Section 5.1.3.4 Data handling for relapses within 30 days of onset of previous relapses or relapses with duration beyond 90 days
				28. Section 5.3 Laboratory parameters derivations
				29. Section 5.5 Rule of exclusion criteria of analysis sets
				30. Section 6 Reference

---

Date	Time point	Reason for update	Outcome for update	Section and title impacted (Current)
			23. Removed analysis of [REDACTED] adverse events over the course of the study	
			24. Updated derivations for PDC and MPR	
			25. Indicted removal of analysis of [REDACTED] adverse events over the course of the study	
			26. Clarified MS history date imputation rules	
			27. Removed severity determination of "linked" relapses	
			28. Added rules for conversion of character to numeric continuous laboratory values	
			29. Removed reference to per-protocol set	
			30. Added Brookmeyer and Crowley reference	

---

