## 2 Statistical methods

### 2.1 Data analysis general information

The statistical analysis outlined in this SAP will be performed by United BioSource LLC (UBC), a Novartis-designated Contract Research Organization (CRO), using SAS® version 9.4 or higher.

The primary analysis will be based on Month 18 data, i.e., all data up to and including Month 18. This analysis will be performed after all participants have completed their Month 18 visit, discontinued study treatment prior to Month 18 (ofatumumab-treated participants) or discontinued the study prior to Month 18 (healthy control participants) (see [Section 2.1.1](#) and [Section 2.13](#) for additional details). The final analysis will include all data through Month 30.

For continuous variables, descriptive statistics will include number of participants (n) with available data, mean, standard deviation, minimum, maximum, median and 25th and 75th percentiles. For categorical variables, frequency counts and percentages will be reported. Where appropriate, 2-sided 95% confidence intervals (CIs) for point estimates of the mean or proportion will be provided.

In general, data summaries will be presented for ofatumumab-treated participants in the relevant analysis set. In instances where data are collected for both ofatumumab-treated participants and healthy control participants, data summaries will be presented **by Cohort** (ofatumumab-treated participants or healthy control participants) and on all participants in the respective analysis set.

All data (collected or derived) will be listed appropriately.

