## 2.2 Analysis sets

The Full Analysis Set (FAS) will include all enrolled participants that received any study drug.

The Safety Analysis Set (SAF) will be the same as the FAS.

The Healthy Control Analysis Set (HCAS) will include all enrolled healthy control participants. This analysis set will be used in the analysis of data collected from healthy control participants.

The modified FAS (mFAS) will include all participants in the FAS except for those who discontinued treatment prematurely prior to Month 18 for reasons other than lack of efficacy or death, or those who completed their Month 18 visit but missed relapse/EDSS/MRI (Gd+ or

new/enlarging T2 lesions) at Month 6, 12 or 18, unless they showed disease activity (i.e., MRI activity after Month 6 through 18 or relapse/3-month clinical disability progression between Months 6 and 18). The mFAS will be used for NEDA-3, NEDA clinical and NEDA radiological efficacy analyses.

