The number of new/enlarging T2 lesions in Months 6 to 18 for each participant = Month 12 value (i.e., Month 12 scan relative to Month 6 scan) + Month 18 value (i.e., Month 18 scan relative to Month 12 scan). Participants are excluded from this calculation if the Month 6 value

(i.e., Month 6 scan relative to baseline scan) is missing. Only participants with a Month 6 value and at least one of the Month 12 or Month 18 values are included in this calculation.

The annualized new/enlarging T2 lesion rate (participant-based) will be summarized descriptively as a continuous variable by Cohort using the FAS or HCAS, as appropriate. The annualized new/enlarging T2 lesion rate (cohort-based), along with its components (i.e., numerator and denominator), will be reported by Cohort using the FAS or HCAS, as appropriate.

The annualized relapse rate (ARR) will be calculated using a participant-based approach and a cohort-based approach as follows:

- **Participant-based approach:**  $[(\text{number of confirmed relapses in Months 6 to 18 for a given ofatumumab-treated participant}) / (\text{number of days in Months 6 to 18 for a given ofatumumab-treated participant})] \times 365.25$
- **Cohort-based approach:**  $[(\text{total number of confirmed relapses in Months 6 to 18 for all participants within the ofatumumab-treated cohort}) / (\text{total number of days in Months 6 to 18 for all participants within the ofatumumab-treated cohort})] \times 365.25$

The ARR (participant-based) will be summarized descriptively as a continuous variable using the FAS. The ARR (cohort-based), along with its components (i.e., numerator and denominator), will be reported using the FAS. The ARR (both participant- and cohort-based) will also be derived through Month 18 and summarized descriptively using the FAS.

The number and percentage of participants with 0, 1, 2 or  $\geq 3$  confirmed relapses in Months 6 to 18 will be presented using the FAS. In addition, the number and percentage of participants with at least 1 confirmed relapse in Months 6 to 18 will be presented using the FAS. Participants with confirmed relapses through Month 18 will be summarized in a similar manner using the FAS.

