The number and percentage of participants achieving 3-month disability worsening-free in Months 6 to 18 will be presented using an observed case approach (completers) using the FAS. The number and percentage of participants achieving NEDA clinical in Months 6 to 18 and NEDA radiological in Months 6 to 18 using the ofatumumab-treated participants derivation described in [Section 2.6.1](#) will be presented using the mFAS. In addition, the number and percentage of participants achieving NEDA radiological in Months 6 to 18 using the ofatumumab-treated and healthy control participants derivation described in [Section 2.6.1](#) will be presented using the mFAS or HCAS, as appropriate. The 2-sided 95% CI for the proportion of participants achieving each of these endpoints will be calculated using an exact method ([Clopper and Pearson, 1934](#)).

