### **2.6.4 Handling of missing values not related to intercurrent event**

For NEDA clinical in Months 6 to 18 and NEDA radiological in Months 6 to 18, the same approach outlined for NEDA-3 in [Section 2.5.4](#) will be followed. For all other secondary endpoints, there is no imputation of missing data planned for this study.

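### The Months 6 to 18 relapse-count table uses the whole FAS with no follow-up condition, so its percentage with at least one relapse is likely to be slightly low

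*SAP*

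**What the plan says.** SAP section 2.6.2 states that the number and percentage of participants with 0, 1, 2 or ≥3 "confirmed relapses in Months 6 to 18 will be presented using the FAS". The percentage with at least one confirmed relapse follows on the same set, and a version through Month 18 is summarized in the same way.

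SAP section 2.2 defines the set: "The Full Analysis Set (FAS) will include all enrolled participants that received any study drug". Nothing in it requires a participant to reach Month 6. SAP section 2.6.4 adds: "For all other secondary endpoints, there is no imputation of missing data planned for this study". SAP section 2.1 says of categorical displays only this: "For categorical variables, frequency counts and percentages will be reported". Its reference to participants with available data is attached to continuous variables.

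Elsewhere in section 2.6.2, the Months 6 to 18 responder and rate summaries for treated participants each deal with follow-up in some way:

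- 3-month disability worsening-free "will be presented using an observed case approach (completers) using the FAS".
- For the annualized T2 lesion rate, "Only participants with a Month 6 value and at least one of the Month 12 or Month 18 values are included in this calculation".
- NEDA clinical and NEDA radiological use the mFAS.
- The participant-based ARR divides by the "number of days in Months 6 to 18 for a given ofatumumab-treated participant", and the cohort-based ARR divides by total days.

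The SAP document history for Amendment 2 records: "Removed observed case approach for summarization of participants with confirmed relapses". The current text agrees with that entry, so no completer rule now applies to the relapse-count table.

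**The concern.** Participants who leave are not replaced (Protocol section 9.1.2), and their data enter the Month 18 analysis (SAP section 2.13). Someone who leaves in Month 2 cannot have a relapse recorded in Months 6 to 18. Someone who leaves in Month 10 can have one recorded for only part of the window. Both are in the FAS denominator. If neither has a recorded relapse in the window, the only row open to them is 0. Leavers who did relapse in the window before leaving are counted correctly.

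The number of confirmed relapses in Months 6 to 18 is a named secondary endpoint of a trial with one treated arm. The percentage with at least one relapse will therefore be read as an absolute 12-month risk. Unlike sampling error, the distortion has a known direction: it makes the relapse frequency look lower than it is.

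**Working it through.** **Inputs from the documents**

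- 100 evaluable participants and 15% dropout (SAP section 3.1). Check: 100 / (1 − 0.15) = 117.6, which rounds up to the plan's 118. That leaves 18 leavers.
- ARR on ofatumumab of 0.11 and 0.10 in the pivotal trials (Protocol section 4.5).

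The plan states no expected value for the relapse-count table itself, so there is no figure of its own to reproduce for that table.

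**Assumptions**

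- Relapse rate r is constant at 0.10 per year, with 0.05 to 0.20 as the range. This trial enrols earlier disease than the pivotal trials, so the rate is illustrative.
- Leavers relapse at the same rate as stayers until they leave, and relapse follow-up ends when they leave.
- Exit is uniform over Months 0 to 18, so one third (6) leave before Month 6 and two thirds (12) leave during the window. Two other timings are shown.

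**Formulas** (the window is 1 year)

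- Chance of at least one relapse with full follow-up: p = 1 − exp(−r).
- Chance of a recorded relapse for someone leaving uniformly within the window: q = 1 − (1 − exp(−r)) / r.
- Whole-FAS percentage: (100p + m·q) / 118, where m is the number leaving within the window (0, 12 or 18).

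**At r = 0.10:** p = 0.0952 and q = 0.0484.

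- All 18 leave before Month 6: 9.52 / 118 = 8.1%, a relative shortfall of 15.3%.
- Uniform over Months 0 to 18: (9.52 + 12 × 0.0484) / 118 = 10.10 / 118 = 8.6%, a shortfall of 10.1%.
- Uniform over Months 6 to 18: (9.52 + 18 × 0.0484) / 118 = 10.39 / 118 = 8.8%, a shortfall of 7.5%.

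| Assumed rate per year | Full follow-up | All leave before Month 6 | Uniform 0–18 | Uniform 6–18 |
|---|---|---|---|---|
| 0.05 | 4.9% | 4.1% | 4.4% | 4.5% |
| 0.10 | 9.5% | 8.1% | 8.6% | 8.8% |
| 0.20 | 18.1% | 15.4% | 16.3% | 16.8% |

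The relative shortfall hardly changes with the rate. It is roughly proportional to dropout: under uniform exit at r = 0.10 it is d × (1 − (2/3) × q/p) = d × 0.661. That gives 10.1% at d = 18/118, and 16.5% if dropout were 25% (an assumed value).

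**Effect of changing only the denominator.** Dropping the 6 who leave before Month 6 gives 10.10 / 112 = 9.0%. This recovers about half of the gap between 8.6% and 9.5%, because the 12 partial follow-ups still count as complete.

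**Through Month 18.** Over 1.5 years, r × 1.5 = 0.15, so p = 13.9%. For the 18 leavers, q = 1 − 0.1393 / 0.15 = 0.0714. The whole-FAS figure is (13.93 + 18 × 0.0714) / 118 = 12.9%, a shortfall of about 7%. Here everyone has follow-up from Day 1, so only partial follow-up is at issue.

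**The case against.** The strongest reply is that the SAP never says that leavers score 0. It names a set and some categories, and with no imputation planned, unfollowed participants could be left as missing. That is fair as far as it goes: zero-scoring is an inference. It is still the natural one. The set is everyone dosed, the lowest category is 0, there is no missing row, and the SAP writes out the completer approach where it wants one, as for disability worsening-free. If the other reading is meant, the denominator is unstated and still has to be written down.

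A reader might go further in two ways, and the documents support neither.

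- *That the table breaks the no-imputation rule in section 2.6.4.* Counting recorded events over everyone treated is an ordinary observed-event count, as in the adverse event tables. No missing value is filled in. The weakness is that follow-up time is ignored.
- *That the participant-based ARR is also biased by people with no days in the window.* For them the formula is 0/0 and yields no value. The rate is summarized as a continuous variable, and section 2.1 reports n with available data for those, so they would drop out visibly. An explicit sentence would be tidy, but no bias is shown.

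It can also be said that the matter is small and partly covered nearby. This stands. At r = 0.10 the shortfall is about 1 percentage point, while the 95% half-width for 9.5% of 118 is 1.96 × √(0.095 × 0.905 / 118) = 5.3 points. No hypothesis is tested. The cohort-based ARR is reported with its numerator and denominator, and NEDA clinical is reported on the mFAS. These limit the consequence but do not correct the percentage in this table.

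**Conclusion.** The point holds in a limited form. Followed as written, the Months 6 to 18 relapse-count table and its percentage with at least one relapse carry a downward bias, because unobserved time is treated as relapse-free time. At the plan's 15% dropout, with uniform exit and a constant rate of 0.10 per year, the percentage is 8.6% instead of 9.5%. The relative shortfall is about 7% to 15%, depending on when leavers exit.

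The size rests on the assumed rate and exit pattern and on leavers relapsing at the same rate as stayers. If leavers relapse more, the bias is larger. The endpoint is secondary and descriptive, no test is affected, and the cohort-based ARR is sound. The finding does not extend to a contradiction with section 2.6.4 or to a bias in the participant-based ARR. It deserves correction because the direction is known, the percentage will be read as an absolute risk, and the remedy is cheap.

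**What to change.** In SAP section 2.6.2:

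1. For the Months 6 to 18 relapse-count table, use FAS participants with follow-up beyond Month 6 as the denominator. Alternatively, keep the FAS and add a row for participants not followed in Months 6 to 18.
2. Add the Kaplan-Meier proportion with at least one confirmed relapse from Month 6 to Month 18, with a 95% CI, censoring at last contact. This step is needed as well, because the first recovers only about half the gap.
3. For the summary through Month 18, keep the full FAS and add only a Kaplan-Meier estimate from Day 1. Do not carry the Month 6 restriction over: it would remove participants who relapsed in Months 0 to 6 and then left.

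The cost is one denominator sentence and two estimates. Relapse dates and the date of last contact are already used elsewhere in the SAP. The downsides are a slightly less favourable percentage and the Kaplan-Meier assumption that censoring is non-informative, which should be stated with the result.

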6.1.4 Treatment duration

The planned duration of treatment is 18 months and participants will continue on ofatumumab treatment arm for 18 months. Once a participant is started on ofatumumab, they must remain on ofatumumab throughout the duration of the study and switching to a different DMT therapy will not be permitted. Participants may be discontinued from treatment earlier due to unacceptable adverse events, disease progression and/or at the discretion of the Investigator or the participant. Additional efficacy and safety assessments will be evaluated during an optional 12-month open-label extension, necessitating ofatumumab monotherapy over the course of up to 30 months in patients that choose to enter the extension.

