### 2.5.1 Primary endpoint(s)

The primary endpoint is NEDA-3 (relapse-free, 3-month clinical disability progression-free, MRI activity-free) in Months 6 to 18 (yes/no). The 3 components of the primary endpoint are defined as follows:

- Relapse-free is defined as no confirmed relapses. Partial relapse start and end dates will be imputed as outlined in [Section 5.1.3.3](#). Criteria for the linking/combining of individual relapses is outlined in [Section 5.1.3.4](#).
- 3-month clinical disability progression-free is defined as no clinical disability progression as measured by EDSS (global assessment scale), where 3-month confirmed clinical disability progression is defined as an increase from Month 6 in EDSS (global assessment scale) sustained for at least 3 months. That is, after a scheduled or unscheduled visit at which the participant fulfills the clinical disability progression criteria as outlined in [Table 7](#), all EDSS assessments (scheduled or unscheduled) need to also fulfill the clinical disability progression criteria until the progression can be confirmed at the first scheduled visit that occurs in the absence of relapse (confirmed or unconfirmed) 3 months after the onset of the progression, or later. If a participant fulfills the clinical disability progression criteria based on the single EDSS assessment at Month 18, it will be considered a confirmed clinical disability progression (sustainment for at least 3 months will not be required). If a participant dies due to MS (i.e., EDSS = 10 at any time), it will be considered a confirmed clinical disability progression regardless of the Month 6 EDSS or change in EDSS.

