### 2.5.3 Handling of intercurrent events

Handling of treatment discontinuations will follow composite variable strategy. For treatment discontinuation prior to Month 18 due to lack of efficacy or death, NEDA-3 and associated endpoints will be considered as “non-response”; if treatment discontinuation prior to Month 18 is due to reasons other than lack of efficacy or death, or if the Month 18 visit was completed but relapse/EDSS/MRI (Gd+ or new/enlarging T2 lesions) was missed at Month 6, 12 or 18, and disease activity was not shown (i.e., MRI activity after Month 6 through 18 or relapse/3-month clinical disability progression between Months 6 and 18), the participant will be excluded from mFAS for all NEDA-3 and associated endpoints efficacy analyses and thusly out of scope for intercurrent events handling; the rest of the participants had disease activities in Months 6 to 18, and NEDA-3 and associated endpoints for those participants will be considered as “non-response”.

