### 2.5.6 Supplementary analyses

The following supplemental analyses of the primary endpoint will be performed:

- An analysis using an observed case approach (completers) using the FAS based on participants who completed their Month 6 and Month 18 visits.

- An analysis using a non-response imputation (NRI) approach using the FAS. NRI will be applied to missing data regardless of intercurrent events. NRI is a conservative imputation method for dichotomous variables. For missing data, the primary endpoint will be imputed as “No”. Refer to [Section 5.1.3.3](#).
- An analysis using the mFAS in which the MRI activity-free component of NEDA-3 is defined as no new/enlarging T2 lesions compared to Month 6 on any MRI scan (scheduled or unscheduled) after Month 6
- An analysis using the mFAS in which the clinical disability progression-free component of NEDA-3 is based on 6-month clinical disability progression-free

For each of the supplemental analyses described above the number and percentage of participants achieving NEDA-3 in Months 6 to 18 will be presented. The 2-sided 95% CI for the proportion of participants achieving NEDA-3 in Months 6 to 18 will be calculated using an exact method ([Clopper and Pearson, 1934](#)).

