### 2.6.1 Secondary endpoint(s)

Secondary efficacy endpoints include the following:

- Number of confirmed relapses in Months 6 to 18
- 3-month disability worsening-free in Months 6 to 18 (yes/no)
- NEDA clinical (relapse-free, 3-month clinical disability progression-free) in Months 6 to 18 (yes/no)
- NEDA radiological (MRI activity-free) in Months 6 to 18 (yes/no) for ofatumumab-treated participants, where MRI activity-free is defined as no Gd+ lesions on any MRI scan (scheduled or unscheduled) after Month 6, or new/enlarging T2 lesions compared to Month 6 on any MRI scan (scheduled or unscheduled) after Month 6
- NEDA radiological (MRI activity-free) in Months 6 to 18 (yes/no) for ofatumumab-treated and healthy control participants, where MRI activity-free is defined as no new/enlarging T2 lesions compared to Month 6 on any MRI scan (scheduled or unscheduled) after Month 6
- Change from baseline, as well as change from Month 6 re-baseline, in the following conventional MRI metrics by time point: Gd+ lesion number, Gd+ lesion volume, T2 lesion volume and T1 unenhancing lesion volume
- Values of the following conventional MRI metrics by time point (baseline or post-baseline, as appropriate): new Gd+ lesion number, T2 lesion number, new/enlarging T2 lesion number, new unenhancing T1 lesion number and new/enlarging T2 lesion volume

- Percent change from baseline and percent change from Month 6 re-baseline in brain volume parameters (whole brain and regional) by time point (also obtained in healthy control participants for normalization purposes)

Note that Gd will not be given to healthy control participants and Gd enhanced T1 MRI imaging will not be conducted in healthy control participants.

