### **2.6.3 Handling of intercurrent events**

For NEDA clinical in Months 6 to 18 and NEDA radiological in Months 6 to 18, the same approach outlined for NEDA-3 in [Section 2.5.3](#) will be followed. For all other secondary endpoints, there is no imputation of missing data planned for this study.

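### The completers-only analysis of 3-month disability worsening-free leaves out confirmed progression and MS death in participants who do not complete Month 18, although the SAP counts the same participants as failures in NEDA clinical

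*SAP*

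**What the plan says.** SAP 2.6.2 states that the number and percentage free of 3-month disability worsening in Months 6 to 18 "will be presented using an observed case approach (completers) using the FAS". It does not define completers. The only explanation is in SAP 2.5.6, for a supplementary analysis of NEDA-3, where the term is "based on participants who completed their Month 6 and Month 18 visits".

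SAP 2.6.3 and 2.6.4 extend the NEDA-3 handling rules to NEDA clinical and NEDA radiological only. Beyond those two, "For all other secondary endpoints, there is no imputation of missing data planned for this study". SAP 2.6.5 and 2.6.6 plan no sensitivity or supplementary analysis of any secondary endpoint.

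Other parts of the SAP treat the same events differently:

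- SAP 2.5.1, in defining progression: "If a participant dies due to MS (i.e., EDSS = 10 at any time), it will be considered a confirmed clinical disability progression", whatever the Month 6 EDSS.
- SAP 2.2: "The mFAS will be used for NEDA-3, NEDA clinical and NEDA radiological efficacy analyses". This set keeps early leavers who showed disease activity, including 3-month progression between Months 6 and 18.
- SAP 2.5.3: "For treatment discontinuation prior to Month 18 due to lack of efficacy or death, NEDA-3 and associated endpoints will be considered as" non-response. Retained early leavers with disease activity are scored the same way.

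Protocol 12.5.1 assigns the FAS to all efficacy analyses and puts no completer restriction on this endpoint. Protocol 6.1.4 shows that leaving can be related to the outcome: "Participants may be discontinued from treatment earlier due to unacceptable adverse events, disease progression and/or at the discretion of the Investigator" or the participant.

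**The concern.** Take a participant whose EDSS rise is first seen at an unscheduled visit in Month 8, is confirmed at the scheduled Month 12 visit, and who leaves in Month 13. In NEDA clinical this is a failure. In the disability endpoint the participant is absent, because Month 18 was not completed. A participant who dies of MS in Month 14 is also a NEDA clinical failure and absent here. If completing means attending Month 18, the MS-death clause of the progression definition can never operate before that visit in this analysis.

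The two components and their composite then rest on three different sets. Confirmed relapses use the FAS without a completer restriction, disability uses completers, and NEDA clinical uses the mFAS. The last two sets are not nested. A Month 18 completer who missed the Month 12 EDSS and showed no activity is outside the mFAS but can be a completer.

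Two things are at stake. The disability table cannot be reconciled with NEDA clinical. And if people who worsen are more likely to leave, the disability proportion flatters the drug, with no other planned analysis of this endpoint to reveal it.

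**Working it through.** **1. Which events are lost.** In Months 6 to 18, SAP Table 3 has EDSS analysis visits at Months 6, 12 and 18. SAP 2.5.1 confirms progression at the first scheduled, relapse-free visit at least 3 months after onset.

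- Onset seen at Month 12 and confirmed at Month 18: the participant is a completer and is counted.
- Onset at an unscheduled visit, confirmed at Month 12, then exit: confirmed but left out.
- Onset at Month 12, confirmed at an early End of Study visit (a nominal visit under SAP 2.1.1): confirmed but left out.
- MS death before Month 18: confirmed by definition but left out.

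**2. The plan's own figures.** SAP 3.1 gives 100 evaluable participants, 15% dropout and 118 enrolled.

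- 100 / (1 − 0.15) = 117.6, rounded up to 118. Reproduced.
- 1.96 × √(0.80 × 0.20 / 100) = 7.8% and 1.96 × √(0.85 × 0.15 / 100) = 7.0%. Reproduced.

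This leaves 118 − 100 = 18 leavers. The documents give neither an expected worsening-free rate nor a split of dropout reasons, so both are assumed below.

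**3. Formula.** Let x of 100 completers be worsening-free and let a fraction r of the 18 leavers worsen.

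- Completers figure: x / 100.
- Figure for all 118: (x + 18(1 − r)) / 118.
- The two are equal when r = 1 − x/100. The completers figure is too high only above that value.

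**4. Illustration with x = 95.**

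- r = 5%: (95 + 17.1) / 118 = 95.0%, overstatement 0.
- r = 10%: (95 + 16.2) / 118 = 94.2%, overstatement 0.8 points.
- r = 15%: (95 + 15.3) / 118 = 93.5%, overstatement 1.5 points.

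**5. Range over whole numbers.** Here k of the 18 leavers worsen, and each cell is (x + 18 − k) / 118, with the completers figure minus that value in brackets.

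| Completers | k = 1 | k = 3 | k = 5 | Break-even k |
|---|---|---|---|---|
| 95/100 | 94.9% (+0.1) | 93.2% (+1.8) | 91.5% (+3.5) | 0.9 |
| 90/100 | 90.7% (−0.7) | 89.0% (+1.0) | 87.3% (+2.7) | 1.8 |
| 85/100 | 86.4% (−1.4) | 84.7% (+0.3) | 83.1% (+1.9) | 2.7 |

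The sign reverses when leavers worsen less often than completers. Five of 18 is 28%, well beyond the 5% to 15% illustrated. Treating all 18 as at risk is generous, because anyone who leaves before Month 6 has no Month 6 EDSS from which to progress.

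**6. Precision.** The Clopper-Pearson 95% interval for 95/100 is 88.7% to 98.4%, much wider than the shifts in step 4.

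**The case against.** The case for leaving the analysis alone has several strong parts.

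- **Most worsening is still counted.** A reader might infer that all worsening before Month 18 is discarded. It is not: only events in participants who fail to complete a required visit are lost. With the EDSS visits in step 1, few leavers can have confirmed progression. MS death is a remote event in people who enter aged 18 to 35 with EDSS 0 to 3.0. This stands.
- **Stopping treatment is not the same as missing Month 18.** A reader might infer that every lack-of-efficacy exit drops out. Protocol 9.1.1 says that participants who stop treatment are not thereby withdrawn and should return for assessments, so some may complete Month 18. Protocol section 3 says that patients must stay on ofatumumab monotherapy to remain in the trial. The two passages point different ways and need to be reconciled, so the inference is not secure.
- **Bias in the drug's favour is not established.** SAP 2.5.1 also counts a single unconfirmed EDSS rise at Month 18 as confirmed progression. That lowers the worsening-free proportion among exactly these completers. This stands.
- **A larger size is tempting.** Adding only failing leavers to the denominator gives 95/(100 + 0.9) = 94.2% to 95/(100 + 2.7) = 92.5%, an apparent overstatement of 0.8 to 2.5 points. That calculation omits leavers who did not worsen. It shows 0.8 points even when leavers and completers worsen at the same 5%, where the true difference is zero. Scoring all 18 leavers as failures gives 95/118 = 80.5%, which is a bound and not an expectation.
- **The stakes are limited.** The endpoint is descriptive, no hypothesis is tested, the method is openly stated, and NEDA clinical reports progression together with relapse. This lowers the priority. It does not supply a disability proportion that includes the missing events.

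None of this answers the inconsistency itself. According to the SAP's document history, Amendment 2 removed the observed case approach for confirmed relapses, yet it remains for disability.

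**Conclusion.** The concern holds as an internal inconsistency with a possible, probably small, upward bias. If completers has the SAP 2.5.6 meaning in SAP 2.6.2, confirmed progression or MS death in a participant who does not complete Month 18 is left out of the disability endpoint and is a failure in NEDA clinical.

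The completers proportion is too high only if leavers worsen more often than completers. That is plausible, because disease progression is a listed reason for stopping treatment, but the documents do not show it. At an assumed 95.0% among 100 completers, with 18 leavers worsening at an assumed 5% to 15%, the overstatement is 0 to 1.5 points. Other assumptions widen this range and can reverse the sign. The change is worth making because the plan offers no other view of this endpoint.

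**What to change.** In SAP 2.6.2:

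- Analyse the endpoint in FAS participants with a Month 6 EDSS. Count any confirmed progression under SAP 2.5.1, or MS death, in Months 6 to 18 as failure whether or not Month 18 was completed. State how an MS death without a Month 6 EDSS is handled, since SAP 2.5.1 counts it regardless of that value.
- Counting failing leavers while dropping the rest would lean low. Censor leavers without observed worsening at their last EDSS and report the Kaplan-Meier estimate at Month 18.
- Give a non-response-imputation version and the completers version as supplementary, and define completers where the term is used.

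Do not move the endpoint onto the mFAS or borrow the NEDA failure rule. That set drops Month 18 completers with full EDSS data who missed an MRI and showed no activity. It keeps other-reason leavers only if they showed activity, which may be a lesion or a relapse, and its rule also fails non-MS deaths. Whether a lack-of-efficacy exit should count as disability worsening is a choice of estimand, not a correction.

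The cost is a short change to SAP 2.6.2, one extra table and possibly a slightly less favourable proportion. No new data are needed, and the progression derivation already exists.
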